13.2 STATISTICAL ANALYSES

Due to the small number of patients enrolled in this study, the data will be analyzed by descriptive statistics and exploratory figures. A statistical analysis plan will be finalized prior to database lock. It is envisaged that analyses will be performed on all available data.

13.3 INTERIM ANALYSIS

An interim analysis will be conducted on all available safety data and any available preliminary efficacy data up to the 3 month time point for Cohort 4 patients. The interim analysis, consisting of descriptive statistics and exploratory figures will be used to provide data to the regulatory authorities and IRB/ethics committees before pediatric patients are enrolled in Cohort 5. Formal statistical tests will not be performed as part of the interim analysis.

13.4 SAFETY ENDPOINTS

13.4.1 Adverse Events

The number and percentage of patients with treatment emergent adverse events (ie, started or increased in severity after the patient received study treatment and includes abnormal lab results, ECGs etc.) will be summarized. The adverse events recorded prior to SAR421869 administration will not be summarized and will be separated from the adverse events that are recorded post SAR421869 administration in the final listings.

An overall summary will include the number and percentage of patients with:

- A fatal AE (death).
- At least one serious AE.
- At least one severe AE.
- At least one related AE.
- Without any AEs.

- An additional table will show the number and percentage of patients with treatment emergent adverse events broken down by System Organ Class, High Level Term and Preferred Term. Related AEs will be summarized separately.
- Specific grouping will be done for ocular events that are inflammatory in nature.

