9.2.2 Intraocular Injection

After informed consent is completed, patients will have baseline assessments and eligibility will be confirmed. Eligible patients will be scheduled for surgery, which will be performed under anesthesia. The study eye will be the eye that in the opinion of the investigator, in consultation with the patient, is the worse seeing eye. In order to select the worse eye the investigator will review the patient historic and Day -1 visual acuity and visual field data and also consider which eye is dominant and any preferences shown by the patient. The study eye will be marked prior to entering the operating room and once in the operating room the study eye will be reconfirmed.

Surgery will be performed under general anesthesia or waking sedation at the surgeon's discretion, with additional periocular/retrobulbar injections according to surgeon and anesthesiologist preferences. Surgery will be performed under sterile conditions in accordance with hospital operating room protocols.

A standard 20- or 23-gauge 3 port pars plana vitrectomy will be performed. If achievable, a posterior vitreous detachment will be induced and the posterior hyaloid will be removed from the posterior retinal surface at least to include the anticipated retinotomy site.

The posterior retina will be examined and the appropriate site for subretinal injection will be identified. Additional details on retinotomy will be provided in study manuals. The final positioning of the retinotomy and subretinal bleb will be determined by the surgeon.

The retina will be approached with a needle loaded with SAR421869. A hydraulically-induced retinotomy will be created and a subretinal bleb created. If the surgeon determines that the bleb is not forming in the correct position, he/she can choose to stop infusing and create another retinotomy. This can be done up to twice until the full volume has been delivered.

At the discretion of the surgeon an air-fluid exchange may be undertaken.

Following the administration of SAR421869, the fundus will be examined by indirect ophthalmoscopy and scleral depression to look for peripheral retinal tears. If there are any peripheral retinal tears, they will be treated with cryopexy and a fluid-air exchange will be done. The vitreous cavity may be filled with the appropriate tamponade at the discretion of the surgeon.

The eye will be patched and the patient will be taken to the post-operative observation area.

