11 OBLIGATIONS OF THE INVESTIGATOR REGARDING SAFETY REPORTING

11.1 ADVERSE EVENT DEFINITION

An adverse event (AE) is any untoward medical occurrence in a patient that develops or worsens in severity during the conduct of a clinical study of a pharmaceutical product and does not necessarily have a causal relationship to the investigational product. This can, therefore, be any unfavorable and unintended physical sign, symptom, or laboratory parameter that develops or worsens in severity during the course of the study, whether or not considered related to the investigational product.

All AEs must be described in the appropriate section of the CRF and their seriousness and putative relationship (causality) to the study medication and/or protocol procedures noted. Adverse events are recorded following signature of the informed consent; this is to ensure that any adverse events associated with the screening procedures are captured.

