7.3.1 Adverse Events

AEs will be coded using MedDRA® (last version available at time of database lock). All reported events for all patients with cohort, event description, event date, resolution date, severity, outcome, relatedness, SAE indication, duration, High Level Term (HLT), System Organ Class (SOC), and Preferred Term (PT) will be listed. Specifically, AEs prior to treatment, treatment emergent adverse events (TEAEs), (i.e., started or increased in severity after the patient receives IMP, including abnormal lab results, ECG, etc.) and TEAEs of special interest will be listed separately. An overall summary table of TEAEs will also be provided that includes the number and percentage of TEAEs and patients with at least one TEAE in each dose cohort with:

- A fatal AE (death)
- At least one serious AE
- At least one severe AE
- At least one AE related to IMP
- At least one TEAE related to procedure
- Without any AEs

In addition, tables will present both the number and percentage of TEAEs and patients with TEAEs by SOC, HLT, PT, severity and cohort. Adverse events of special interest (AESI), detailed in the protocol, will be summarized by SOC, HLT, PT, severity and cohort. AESIs will be indicated, where appropriate in the patient profile listing of AEs. AEs related to the IMP and serious adverse events (SAEs) will be indicated in the AE listing and described in detail in the body of the report. Specific grouping will be done for events inflammatory in nature in the eye. Summary tables will be presented both with the inflammatory events grouped and without the events grouped. All events with the following preferred terms will be considered inflammatory in nature in the eye:

- Anterior chamber cell
- Anterior chamber inflammation
- Choroidal effusion
- Conjunctivitis
- Eye inflammation
- Eye discharge
- Keratitis

- Macular oedema
- Subretinal fluid
- Uveitis
- Vitreous floaters

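### Treatment emergence starts at receipt of the product, so a complication of anesthesia or vitrectomy that begins before injection and does not worsen falls outside the TEAE tables, including the procedure-related one

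*Protocol*

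**What the plan says.** Protocol 13.4.1 defines a treatment-emergent event as one that "started or increased in severity after the patient received study treatment". SAP 7.3.1 uses the same clock: "started or increased in severity after the patient receives IMP". Protocol 13.4.1 then adds: "The adverse events recorded prior to SAR421869 administration will not be summarized". Such events are kept apart in the final listings.

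Collection starts much earlier. Protocol 11.1 says: "Adverse events are recorded following signature of the informed consent". Protocol 11.6 asks the investigator to judge causality to the study procedure as well as to the product.

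Protocol 9.2.2 gives the order of surgery. It is done under anesthesia, and "A standard 20- or 23-gauge 3 port pars plana vitrectomy will be performed". Then: "The retina will be approached with a needle loaded with SAR421869. A hydraulically-induced retinotomy will be created and a subretinal bleb created". Finally: "Following the administration of SAR421869, the fundus will be examined by indirect ophthalmoscopy and scleral depression to look for peripheral retinal tears".

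The procedure-related outputs draw on TEAEs only. SAP 7.3.1 lists "At least one TEAE related to procedure" as a summary line. Tables 3A and 3H in SAP 8.3.1 follow it, as does Table 3G in the August 2019 memorandum that replaces the SAP's list of outputs.

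**The concern.** The product reaches the eye only through this operation, and safety and tolerability are the primary objective. Procedural harm is thus part of what the study has to describe, and the plan collects procedure causality for that purpose. Yet the clock starts at the product and not at the operation. Events with the clearest link to surgery, those occurring before any vector is given, are grouped with screening-period events and kept out of the table meant to show procedural harm.

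The by-cohort AE tables also go to the DSMB: SAP 8.0 puts the outputs of Sections 8.1 to 8.4.2 into its reports as a minimum. With three patients in a cohort, one misplaced patient visibly changes a row.

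**Working it through.** The plan states no event rate, sample size calculation or target precision, so there is no figure of its own to reproduce. The check follows one event through the rules and then sizes the effect.

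**Step 1. Classify the event.** Take a hemorrhage during vitrectomy, or an anesthetic event, that starts before injection and does not worsen.
- Onset test (protocol 13.4.1, SAP 7.3.1): it did not start or increase after the product was received, so it is not a TEAE.
- Recording test (second sentence of protocol 13.4.1): if recorded before administration, it is not summarized.

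**Step 2. Follow it through the outputs.**

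| Output | Includes the event? |
|---|---|
| TEAE tables by SOC and PT, AESI table, inflammatory-event table | No |
| Procedure-related TEAE table (SAP 3H; 2019 list 3G) | No |
| No-events row of Table 3A | The patient could be counted here if there is no TEAE of any kind |
| Listing of pre-treatment events (SAP 3I; 2019 list 3H) | Yes; the SAP shell has no surgery date and no relatedness column |
| Surgery listing (2019 list 2H) and patient profile (SAP 9) | Yes, patient by patient |
| Deaths (protocol 13.6.3) | Included in the AE summary with no TEAE condition |
| SAE table (2019 list 3D) | Unclear: the title has no TEAE limit, but companion listing 3K does |

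**Step 3. Note where the two tests disagree.** A tear made during vitrectomy but found in the examination after injection fails the onset test, yet it is not recorded before administration. The AE listing shells show dates without clock times, and no Day 0 rule is given, so the handling of same-day events is undefined.

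**Step 4. Size.** Assume that the pre-injection event is the patient's only procedure-related event. The denominators are those of the 2019 AE shell, 3 per cohort and 9 in all.
- One cohort: 1/3 − 0/3 = 33.3 percentage points.
- All cohorts: 1/9 − 0/9 = 11.1 points.
- Exact (Clopper-Pearson) 95% interval at N = 9, the 95% level being my choice: for 0/9 the upper limit is 1 − 0.025^(1/9) = 33.6%; for 1/9 the interval is 0.3% to 48.2%.
- At the protocol's Part A totals of 15 and 24 patients, one patient is 1/15 = 6.7 points and 1/24 = 4.2 points.

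**Step 5. How likely is at least one such patient?** The documents give no rate, so this is a range of assumed per-patient risks p, using 1 − (1 − p)^n.

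| p (assumed) | n = 3 | n = 9 |
|---|---|---|
| 2% | 5.9% | 16.6% |
| 5% | 14.3% | 37.0% |
| 10% | 27.1% | 61.3% |
| 20% | 48.8% | 86.6% |

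**The case against.** The best defense is that nothing is hidden. Events are collected from consent, with procedure causality, and pre-treatment events are listed by patient and cohort. The patient profile has fields for surgical complications and for retinal tear, and its AE table has a column for relation to surgery. SAP 6.3 promises that DSMB reports will contain all data collected. With nine patients, a reader of the listings would see every such event. The SAP shells even suggest a sensible intent: the pre-treatment listing is anchored on the enrollment date, and the TEAE listing on the surgery date with a relation-to-surgery column. The present clock also matches the primary endpoint in protocol 6.1, which counts events after the dose.

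Most of this stands, and it limits the effect to tabulation; detection is not impaired. It does not remove the gap, because no rule says that surgery-day events count from the surgery, and the literal text says otherwise.

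A reader might go further and infer that surgical events vanish from every AE summary. The documents do not support that. Deaths enter the summary regardless, the 2019 SAE table title is not limited to TEAEs, and any event that worsens after injection is a TEAE. A reader might also place the retinotomy before the product. Protocol 9.2.2 describes retinotomy and bleb formation with the loaded needle, so those events are not clearly excluded, nor are peripheral tears found in the later examination.

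**Conclusion.** The concern holds in a limited form. As written, a complication of anesthesia or vitrectomy that begins before injection and does not worsen is left out of the TEAE-based summaries, including the procedure-related table.

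The 33-point and 11-point shifts apply only if the patient has no other procedure-related event. Being counted as having no events needs more: no TEAE at all. How often this would arise cannot be derived from the documents. For same-day events, the exclusion follows from the literal rule; how they would be classified in practice is not defined.

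The listings keep this from being serious. It should still be corrected, because safety is the primary objective, the cohorts are very small, and the affected table exists to show procedural harm.

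**What to change.** In protocol 13.4.1 and SAP 7.3.1, define treatment-emergent as onset or worsening from the start of the Day 0 surgical procedure (anesthesia). Count Day 0 events as treatment-emergent unless documented as starting before that point. Use onset as the single test, and drop the separate test based on when the event was recorded.

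Alternatively, keep the present definition and add a by-cohort table of procedure-related events regardless of onset relative to injection.

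If the definition changes, align three further places: the endpoint wording in protocol 6.1 (with the synopsis and SAP 5.1), which now counts from the dose; Table 3D in the 2019 list; and Listing 3K in the same list, so that table and listing cover the same SAEs.

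The cost is a few sentences and one programming rule. The Day 0 rule works from event dates, so clock times are needed only where a site documents an earlier start. Day 0 events are already collected, and no clinical procedure changes.

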13.4.2 Ophthalmological Safety Endpoints

Changes in other safety endpoints will be summarized at each visit; in addition, where appropriate, individual profile plots and mean plot of changes in the variable against time will be presented. The primary time points will be considered the 48-week (12-month) visit; the individual change at this time point only will be plotted against dose received.

13.4.3 Secondary Endpoints

Secondary endpoints will be summarized at each visit; in addition, where appropriate, individual profile plots and mean plot of changes in the variable against time will be presented. The primary time points will be considered the 24-week (6-month) and 48-week (12-month) visit; the individual change at this time point only will be plotted against dose received.

13.4.4 Immunology Endpoint

The number and percentage of patients with antibody response to SAR421869 administration at all time-points will be tabulated.

13.4.5 Laboratory Parameters

Hematology, biochemistry and other laboratory data will be listed at each time point by treatment cohort and, for appropriate values, will be flagged as 'High' or 'Low' if outside the laboratory normal range.

An additional listing will be provided for those patients who have laboratory values that are abnormal and considered to be clinically significant. Laboratory values that become abnormal will also be recorded as an adverse event.

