6.2 SECONDARY ENDPOINTS

The primary time points will be considered the 6- and 12-month visits.

To determine a delay in retinal degeneration following subretinal injection of SAR421869 through changes in function relative to the untreated contralateral eye utilizing the following retinal analytical techniques:

- Best-corrected visual acuity (BCVA).
- Contrast sensitivity.
- Indirect ophthalmoscopy.
- Visual function questionnaire VFQ-25/ CVAQC (when possible).
- Full dilated slit-lamp examination.
- Fundus photography – Panretinal photomontage.

- Visual field testing: Semi-automated Kinetic Perimetry (SKP) and Full-Field German Adaptive Thresholds Estimation (GATE) Static Perimetry, and microperimetry.
- Autofluorescence.
- Electroretinogram (ERG).
- Optical coherence tomography (OCT).

Adverse Events

The number and severity of any adverse events associated with SAR421869 administration will be assessed at each time point.

Immunology Endpoint

Humoral antibody response to SAR421869 administration.

Clinical Laboratory Tests

Hematology, biochemistry, urinalysis and other laboratory data will be measured at various time points throughout the study. Values will be flagged as High or Low if outside the laboratory normal range. Out of range values will be assessed as clinically significant (CS) or not clinically significant (NCS) by the investigator. CS out of range values will be recorded as adverse events. Blood for immunology and blood for PCR will also be taken at multiple time points throughout the study, as will urine samples for biodistribution assessment.

Biodistribution Endpoint

SAR421869 distribution in blood and urine will be assessed by polymerase chain reaction (PCR).

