13.4.6 Other Safety Parameters

All other safety parameters (vital signs, physical examination, ECG) will be listed by patient, treatment assignment, and cohort. New abnormalities will be recorded and summarized under adverse events.

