5.3.2 Clinical Laboratory Tests

Hematology, biochemistry, urinalysis and other laboratory data will be measured at various time points throughout the study. Values will be flagged as High or Low if outside the laboratory normal range. Out-of-range values will be assessed as clinically significant (CS) or not clinically significant (NCS) by the investigator. CS out-of-range values will be recorded as adverse events. Blood for immunology and blood for PCR will also be taken at multiple time points throughout the study, as will urine samples for biodistribution assessment.

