7.3.6 Laboratory Parameters

Clinical laboratory results, including hematology (WBC, RBC, hemoglobin, hematocrit, mean corpuscular volume, mean corpuscular hemoglobin, red cell distribution width, platelets, neutrophils, lymphocytes, monocytes, eosinophils and basophils), blood chemistry (phosphorus, calcium, sodium, chloride, bicarbonate, potassium, fasting blood glucose, creatine phosphokinase, lactate dehydrogenase), kidney and liver function tests (creatinine, blood urea nitrogen, uric acid, alanine aminotransferase (ALT), aspartate aminotransferase (AST), total bilirubin, alkaline phosphatase, total protein, albumin, gamma glutamic transpeptidase, cholesterol), coagulation (prothrombin time and partial thromboplastin time) urinalysis (color, appearance, specific gravity, pH, protein, glucose, ketones, blood, bilirubin, microscopy), and urine pregnancy test (for females of childbearing age) will be listed for each patient and visit in the patient profiles. Individual lab values will be flagged as 'High' or 'Low' if outside the clinical site's normal ranges. A summary of the number of patients with abnormal and/or clinically significant laboratory values will be provided. The following laboratory values and thresholds will be highlighted to indicate their clinical significance for major functions:

- WBC above 2ULN (upper limit of normal)
- Neutropenia < 1500
- Platelets < 100,000
- Creatinine > 1.5ULN
- ALT \geq 3ULN
- AST \geq 3ULN
- Total bilirubin \geq 2 ULN

The lab values will be graded by site physicians, and clinically significant abnormal lab values will also be recorded as AEs.

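### Protocol 13.4.5 makes any laboratory value that becomes abnormal an adverse event, while Protocol 6.2 and SAP 5.3.2 and 7.3.6 require clinical significance, so the any-TEAE and no-AE counts depend on the rule a site follows.

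*Protocol*

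**What the plan says.** The two documents give these rules for turning a laboratory result into an adverse event (AE):

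- **Protocol 13.4.5:** "Laboratory values that become abnormal will also be recorded as an adverse event". The sentence just before it reads "An additional listing will be provided for those patients who have laboratory values that are abnormal and considered to be clinically significant", so clinical significance is attached to the extra listing and not, as written, to AE recording.
- **Protocol 6.2, Clinical Laboratory Tests:** "Out of range values will be assessed as clinically significant (CS) or not clinically significant (NCS) by the investigator", followed by "CS out of range values will be recorded as adverse events".
- **SAP 5.3.2:** "CS out-of-range values will be recorded as adverse events".
- **SAP 7.3.6:** "The lab values will be graded by site physicians, and clinically significant abnormal lab values will also be recorded as AEs".
- **Protocol 13.4.1 and SAP 7.3.1:** both define a treatment-emergent AE (TEAE) so as to include abnormal laboratory results, without mentioning clinical significance.
- **Protocol 11.1:** the general AE definition covers an unfavourable laboratory parameter that develops or worsens, and states no test of clinical significance.

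AE incidence over 12 months is the first item of the primary endpoint (Protocol 6.1, SAP 5.1). The overall summary in Protocol 13.4.1 and SAP 7.3.1 includes the number of patients with no AE.

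**The concern.** Take a value that was normal before dosing, falls outside the range afterwards, and is judged not clinically significant. Under 13.4.5 it is an AE. Under 6.2 it is not among the values named for AE recording. If 13.4.5 governs, the investigator's classification has no bearing on AE status.

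The SAP cannot repair this at the analysis stage. AEs are entered at the sites under the protocol, and the analysis counts what was entered. SAP 7.3.6 also flags values against each clinical site's own normal ranges, so a site working to 13.4.5 would generate events from its own cut-offs.

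Cohorts are small. The AE table shell attached to the SAP has three patients per cohort and nine in all, so one patient moves a cohort's incidence by 1/3, or 33 percentage points. A difference in recording practice between sites could look like a difference between doses.

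**Working it through.** The documents give no expected AE rate and no sample size calculation (Protocol 13.1), so there is no planned figure to reproduce. The conflict rests on the wording. The arithmetic below only indicates scale.

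**Post-dose blood values per adult**, counted from the footnotes to the schedules in Protocol section 2. Fasting glucose and cholesterol are taken at screening only, coagulation is not repeated after dosing, and urinalysis is left out.

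- Haematology 13, chemistry 8, kidney 3, liver 7.
- Weeks 4, 24 and 48: 13 + 8 + 3 + 7 = 31 per visit.
- Day 1, without kidney function: 13 + 8 + 7 = 28.
- Total: 28 + 3 × 31 = 121.

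**Assumptions, none of them from the documents.** Each value is out of range with probability p = 1%, 2.5% or 5%. A share c = 1% to 10% of out-of-range values is judged clinically significant. The effective number of independent values, m, is 121 if all are independent, or 40 as an allowance for correlated analytes.

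**Formulas** for the probability that a patient has at least one laboratory AE:

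- Any abnormal value (13.4.5): 1 − (1 − p)^m
- Clinically significant only (6.2, SAP 5.3.2 and 7.3.6): 1 − (1 − pc)^m

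| m | p | Any abnormal | Significant only, c = 1% | c = 5% | c = 10% |
|---|---|---|---|---|---|
| 121 | 1% | 0.704 | 0.012 | 0.059 | 0.114 |
| 121 | 2.5% | 0.953 | 0.030 | 0.140 | 0.261 |
| 121 | 5% | 0.998 | 0.059 | 0.261 | 0.455 |
| 40 | 1% | 0.331 | 0.004 | 0.020 | 0.039 |
| 40 | 2.5% | 0.637 | 0.010 | 0.049 | 0.095 |
| 40 | 5% | 0.871 | 0.020 | 0.095 | 0.182 |

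Two entries worked through: 1 − 0.99^40 = 0.331, and 1 − (1 − 0.05 × 0.10)^121 = 1 − 0.995^121 = 0.455.

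For nine patients, the expected number with a laboratory AE runs from 9 × 0.331 = 3.0 to 9 × 0.998 = 9.0 under 13.4.5, and from 9 × 0.004 = 0.0 to 9 × 0.455 = 4.1 under the narrower rule. The two ranges overlap only when different assumptions are compared. For the same p and m, pc is smaller than p, so the 13.4.5 share is always the higher one.

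**The case against.** The strongest reply is that 13.4.5 has merely lost a qualifier. Its sentence follows one about clinically significant values, SAP 7.3.6 has a near-identical sentence with the condition present, and the classification step in 6.2 would serve no purpose for AE recording if every abnormal value counted. Three statements support the narrower rule, and nothing in the documents shows a site working to 13.4.5. This is probably what was intended, and it makes the repair easy. It does not remove the conflict: the condition is absent from 13.4.5 as written, and both TEAE definitions omit it too, including the SAP's own.

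The calculation is also open to challenge. Values already abnormal before dosing do not become abnormal, abnormalities persist from visit to visit, and analytes such as haemoglobin and haematocrit move together. That stands, and is why a range is given.

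Three stronger readings are tempting and are not supported:

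- **Nearly every patient would have a laboratory AE.** This holds only towards the top of the assumed range. With 40 effective values and p = 1% the share is 33%.
- **AE incidence would say nothing about dose.** Protocol 13.4.1 and SAP 7.3.1 also report serious, severe and related events, a breakdown by organ class and preferred term, and grouped ocular inflammatory events. The final table list adds separate tables for events of special interest. Apart from added laboratory rows, and possibly some related-event counts (Protocol 11.2 treats an event as related unless a listed test rules it out), these are largely unaffected.
- **Protocol 13.4.6 has the same fault.** It says "New abnormalities will be recorded and summarized under adverse events", but it covers vital signs, physical examination and ECG, whereas 6.2 and SAP 5.3.2 and 7.3.6 concern laboratory values. They do not conflict with it.

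**Conclusion.** The concern holds as an inconsistency in current text that reaches part of the first primary endpoint. The exposed quantities are mainly the incidence of any TEAE and the count of patients without an AE. On the stated assumptions the share of patients with a laboratory AE is about 33% to over 99% under 13.4.5, and under 1% to about 46% under the clinically-significant-only rule. The direction is certain under any common assumption. The size is illustrative, because the out-of-range rate, the share judged significant and the effective number of values are all assumed. The count of 121 applies to adults; in patients under 18 the post-dose safety bloods may be omitted unless clinically indicated. The study is descriptive and no test or sample size depends on this, so it should be corrected but does not undermine the design.

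**What to change.** State one rule throughout:

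- **Protocol 13.4.5:** replace the sentence with *Out-of-range values judged clinically significant will also be recorded as adverse events*.
- **Protocol 13.4.1 and SAP 7.3.1:** add the same qualifier to laboratory results in the TEAE definition.
- **Keep** the listing of laboratory values with high and low flags in 13.4.5, so that out-of-range values judged not significant remain visible.
- **Leave 13.4.6 unchanged.**

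The cost is three short wording changes across the two documents, with no new data, visits or analyses. Where events have already been recorded, the study report should say which rule each site applied.
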